#### 6.1.1 Number of Participants

The proposed sample size is 30. As the primary goal is to assess feasibility and acceptability, not effectiveness, sample size is not based on anticipated effect sizes. Previous guidance has indicated our proposed sample size is an acceptable number for feasibility studies. This sample size will allow us to estimate the retention rate to within a 95% confidence interval of +/- 12% (calculated assuming a retention rate of 85%). Although exploratory only, the sample size will further allow us to detect moderate effect sizes in the continuous outcomes (Cohen's  $d = 0.53$ ) with 80% power ( $\alpha = .05$ , two-tailed) using paired t-tests.

Based on our prior work recruiting from the same population using identical eligibility criteria, we estimate that 40 prospective participants will need to be screened to achieve our sample size.

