### **7.1.5 Reaction Management**

Though the text message content is positive and affirming, mention of stigma may distress some participants. During the intervention orientation, participants will be provided a list of external counseling and support resources they can access if they feel distressed. These resources will also be shared in a text message during the intervention, along with a text message that the messaging exchange will not be monitored and participants should reach out to the suggested resources if they feel distressed.

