## 7.2.5 Study Visits

### Baseline visit (1-1.5 hours)

- Study staff completes informed consent process with participant
- Participant completes CASI baseline survey

- Study staff reviews orientation script with participant
- Participant completes participant locator form
- Participant is enrolled to receive text message intervention

Follow-up visit (1-1.5 hours)

- Participant completes CASI follow-up survey

Telephone interview (30 minutes)

- Select participants (n=12) complete follow-up telephone interview

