### **8.9 Data Safety Monitoring Plan**

Reporting of AEs and SAEs. Adverse incidents will be reported to the UNC Institutional Review Board and NIH project officers. Potential incidents may include protocol violations, security incidents, breach of confidentiality, or adverse psychological reactions to the intervention.

In case of any adverse event, site study staff will record the incident in the adverse event tracking log and report the incident in writing via email to the PI and mentor within 24 hours of discovering the adverse event. Any adverse events or protocol violations will also be reported to the UNC IRB and NIH within 5-10 days (depending on severity and needed information collection) with follow-up reporting of any pending information, action, or follow-up.

All SAEs will be reported by the PI to the IRB as soon as possible and reported to NIDA within 24 hours of the event by email. A written follow-up must be received by NIDA within 72 hours of the event. The written follow-up will include the date of the event, what occurred, actions taken by project staff, planned follow-up (if any), whether the event appears to be related to the intervention or participation in the study, and whether the participant will continue in the study.

All AE/SAE will also be included in the annual report to NIDA.

Reporting of IRB Actions to NIDA. IRB actions will be reported by the PI to NIDA within 5 working days.

Reporting of Changes or Amendments to the Protocol. Changes or amendments to the protocol will be reported to NIDA within 5 working days.

Process of AE/SAE Collection. Serious adverse events are based on the FDA definition and defined as those that result in death, are life-threatening, result in hospitalization or prolongation of existing hospitalization, a persistent or significant disability, a congenital abnormality or birth defect. Other injuries or medical events may be considered to be serious adverse events when, in the opinion of a physician, they may jeopardize the participant and may require medical or

surgical intervention to prevent one of the above outcomes. For the purposes of this study, substance abuse or dependency alone in the absence of other adverse impact will not be considered to be an adverse event.

**AE/SAE Follow-up Plan.** Reports on AEs and SAEs will be reviewed yearly by the PI, mentor, and co-investigators and included in annual reports to the IRB and NIDA. *See Section 4.2 above for details on AE/SAE reporting.*

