Additionally, study staff will remind participants to report any physical or social harm to the study staff immediately, so that participants may receive counseling or other assistance. When necessary, referrals to a psychiatrist or physician will be made.

**Responsibility for Data and Safety Monitoring.** The PI and mentor are ultimately responsible for data and safety monitoring. The QA processes above ensure that the PI and mentor will be aware of important study-related issues on a weekly basis. The PI will monitor all day-to-day study procedures. If an adverse event occurs, the PI will immediately report the event to the mentor, or in her absence, co-investigator [name], mPI of the parent grant.

We will establish a safety monitoring committee (SMC) comprising at least three people. The SMC will meet at the outset of the study in person then semi-annually by telephone or in person. The semi-annual SMC meeting will assess whether study objectives are being met and will ensure that benefit exceeds harm. The SMC will review the protocol, assessments, and consent forms prior to study initiation. The SMC will receive all reports of AEs at the same time that the AEs are forwarded to the UNC IRB. Severe AEs will trigger an immediate meeting of the SMC. Additional meetings of the SMC can be scheduled, as needed, to discuss and resolve AE issues. Members of the SMC will include at least one representative of local health departments, one substance use treatment professional, and one representative of the substance use research community. The SMC will submit minutes following every meeting to the UNC IRB.

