## **8.15 Publication Plan**

Per NIH policy ("Final Rule"), trial results must be published to ClinicalTrials.gov no later than 12 months from the study completion date. The Final Rule requires that results information consist of tables of information summarizing: 1) participant flow information, 2) demographics and baseline characteristics of the enrolled participants, 3) primary and secondary outcomes, including results of any scientifically appropriate statistical tests, and 4) adverse events.

Adverse event information consists of one table that summarizes all serious adverse events experienced by participants enrolled in the clinical trial, and a second table that summarizes other adverse events that exceed a frequency of 5 percent in any arm of the clinical trial. The Final Rule adds a third table for summarizing all-cause mortality, with the number and frequency of deaths due to any cause by arm.

A summative manuscript detailing trial feasibility, acceptability, and preliminary effectiveness outcomes will be written and submitted to the peer-reviewed substance use or mHealth literatures. To standardize reporting, the manuscript will adapt the CONSORT 2010 extension to pilot and feasibility studies following guidelines for adaptation in non-randomized studies described by Lancaster & Thabane (2019). The intervention will be described using the TIDieR checklist and guide. The manuscript will be submitted to a peer-reviewed journal within 12 months of study completion.

Findings will also be disseminated to the public during the principal investigator's dissertation defense, and a report summarizing primary results may be shared with stakeholders in the study community.

No participant names or other identifying information will be used in any dissemination materials (published or otherwise).

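### No systematic adverse event enquiry is specified, and the other sources of harm data are not linked to the adverse event log, so the safety tables are at risk of under-ascertainment

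*Combined protocol and SAP*

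**What the plan says.** **How harms reach staff.** Section 8.9 (Data Safety Monitoring Plan) says that "study staff will remind participants to report any physical or social harm to the study staff immediately", so that counselling or other help can be offered. Staff then log the event and "report the incident in writing via email to the PI and mentor within 24 hours of discovering the adverse event". The part of 8.9 on the process of AE/SAE collection defines seriousness and excludes substance use alone. It does not say how or when events are sought.

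**Which harms are foreseen.** Section 8.9 lists among potential incidents "breach of confidentiality, or adverse psychological reactions to the intervention". Section 3.3.1 foresees distress from survey questions and from messages, and disclosure of drug use if someone else reads the phone.

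**Contact during the four weeks.** Section 7.1.5 says participants are told that "the messaging exchange will not be monitored". The weekly survey in 7.1.3 is anonymous and rates message effectiveness. Section 7.2.1 schedules no visit between day 0 and days 28-35.

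**Follow-up.** Section 7.2.5 lists one task for that visit: "Participant completes CASI follow-up survey". The outcome scales and user items in 7.1.3 include privacy concern and open comments. None asks whether distress, disclosure or hospitalization happened.

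**What is to be reported.** Section 8.15 describes a table of all serious adverse events, "a second table that summarizes other adverse events that exceed a frequency of 5 percent in any arm of the clinical trial", and adds: "The Final Rule adds a third table for summarizing all-cause mortality". Section 7.3 mentions no adverse event analysis or denominator.

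**The concern.** The two foreseen harms of the intervention itself, distress from a message and disclosure to someone who sees the phone, happen away from staff. Following the protocol as written, such an event reaches the log mainly if the participant reports it or staff happen to notice it. The reminder names physical and social harm but not psychological harm, although 8.9 counts psychological reactions as reportable.

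With passive ascertainment, a short event table can mean few events or few questions, and the reader cannot tell which. With 30 participants the 5% threshold turns on one or two reports, so a single missed report can remove an event from the table.

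**Working it through.** The plan gives no expected event rate, capture fraction or safety precision, so it has no figure of its own to reproduce. The steps below show how sensitive the 5% table is.

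**Inputs from the protocol**
- n = 30 (Section 6.1.1: "The proposed sample size is 30").
- Threshold: above 5% (8.15). It applies to non-serious events only; all serious events and deaths are tabulated regardless.
- Retention assumed in the sample size section: 85%, so 0.85 × 30 = 25.5 seen at follow-up.

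**Assumed inputs (not in the documents)**
- True proportion with a given event, p: 5%, 10%, 15%, 20%.
- Fraction of affected participants whose event reaches the log, c: 100%, 75%, 50%, 25%. A value of 85% is added for perfect enquiry among attendees and no capture from anyone else.

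**Step 1. Smallest count above 5%.** 1/30 = 3.3% and 2/30 = 6.7%, so 2 participants are needed. The same holds with 25 or 26 as denominator (1/25 = 4.0%, 2/25 = 8.0%; 1/26 = 3.8%, 2/26 = 7.7%).

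**Step 2. Chance that the event is listed.** Recorded cases X are taken as binomial with n = 30 and probability q = p × c. Then

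P(X ≥ 2) = 1 − (1 − q)^30 − 30 q (1 − q)^29.

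For p = 10%:
- c = 100%, q = 0.10: 1 − 0.042 − 0.141 = 0.82.
- c = 50%, q = 0.05: 1 − 0.215 − 0.339 = 0.45.
- c = 85%, q = 0.085: 1 − 0.070 − 0.194 = 0.74.

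| True rate | c = 100% | c = 85% | c = 75% | c = 50% | c = 25% |
|---|---|---|---|---|---|
| 5% | 45% | 37% | 31% | 17% | 5% |
| 10% | 82% | 74% | 67% | 45% | 17% |
| 15% | 95% | 91% | 87% | 67% | 31% |
| 20% | 99% | 97% | 95% | 82% | 45% |

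**Step 3. What zero recorded events would exclude.** The exact upper limit on q for 0 of 30 is 1 − 0.05^(1/30) = 9.5% (one-sided 95%), or 1 − 0.025^(1/30) = 11.6% (two-sided 95%). The limit on the true rate is that value divided by c. One-sided, it is 9.5% at full capture, 9.5/0.85 = 11.2% at 85%, and 9.5/0.5 = 19% at 50%.

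**Step 4. Serious events.** The threshold does not affect these, but ascertainment does. Section 8.9 requires a report to NIDA within 24 hours of the event and a written follow-up within 72 hours of it, whereas internal reporting runs from discovery. A hospitalization first learned of at day 28-35 could already be past the NIDA limits. For participants who do not return, the documents name no source for the mortality table.

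**The case against.** A reader might infer that harms are captured only if participants volunteer them. The documents do not support that. Survey administrators are trained to recognize distress (3.3.1). Everyone surveyed at post-test is asked about privacy concern, whether the messages made them feel better about themselves, and what they disliked (7.1.3). A completion/discontinuation form is filled in for each participant (7.2.6). Up to 12 participants have a telephone interview, as late as day 49 (7.2.1). What remains is narrower: observation covers the survey sessions only, the form records reasons for leaving, and no source is linked to the log.

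A reader might also infer that the safety result will be an undercount of a known size. That is not shown. Under-ascertainment is the likely direction, but every rate and capture fraction above is an assumption. Full capture is also not what follow-up questions deliver, because they reach only attendees.

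Two further inferences fail. Unmonitored messaging is not a contradiction: it is disclosed, and support resources are given at orientation and by text. Nor does the plan make safety a condition for later trials: Section 5.2.1 ties those to feasibility, acceptability and preliminary effectiveness.

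It is also fair that the adverse event log, case report forms and SOPs are cited but not reproduced, and that a safety monitoring committee reviews the assessments before the study starts. An enquiry may exist in those papers. Even so, Section 8.9 is where it belongs, and the visit list and the listed items omit it.

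**Conclusion.** The point holds as a gap in ascertainment. The protocol describes event tables but no systematic way of finding events, and it leaves its other sources unconnected to the log. The size of any undercount cannot be computed from the documents.

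The calculation shows that the 5% table is fragile at n = 30. For an assumed true rate of 10%, the chance of listing runs from 82% at full capture to 17% at 25%, and a difference in the same direction appears at every rate examined. This rests on the assumed rates and capture fractions, on independence between participants, and on capture being unrelated to anything but chance. For a four-week pilot of 30 this is a cheap improvement worth making and does not invalidate the design.

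**What to change.** 1. Add two or three fixed questions for everyone at the existing day 28-35 visit: distress from messages or surveys, unintended disclosure or social harm, and hospitalization since baseline.
2. State in Section 8.9 that positive answers, and harms found through staff observation, the privacy and open-ended items, the completion form and the interviews, go to the adverse event log for assessment under that section.
3. In Section 7.3 or 8.15, report solicited and volunteered events separately, with exact confidence intervals. For solicited events use the number asked as denominator. State the source for the mortality table among those not seen at follow-up.
4. Reconcile the limits in 8.9 that run from the event with those that run from discovery, for events first learned of at follow-up.

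**Cost.** A few survey items and no new visit. More events will be counted and reported to the IRB, NIH and the safety monitoring committee. Section 8.10 requires approval from both the IRB and the NIDA program officer before the change takes effect. The questions do not reach non-attenders: at 85% retention, with nothing captured from the rest, a 10% event is listed with about 74% probability, and zero of 30 excludes rates above about 11% (one-sided 95%) rather than 9.5%.

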## **8.10 Study Modification**

Given the brief duration of the intervention, it is not expected that modifications to the protocol will be made during the study. Any modifications will be reported to the UNC-Chapel Hill IRB and NIDA program officer. Changes will not be implemented until approval is received from both parties.

## **8.11 Study Discontinuation**

In consultation with NIDA and the UNC IRB, the trial may be stopped if unexpected issues arise suggesting that the intervention or research procedures are causing harm to participants.

## **8.12 Study Completion**

The study completion date is the date of the last instance of data collection from a trial participant, i.e., the date of the last follow-up survey or exit interview, whichever comes last. The research team will notify the IRB of study completion within 30 days of this date.

## **8.13 Conflict of Interest Management Plan**

UNC-Chapel Hill researchers are required to complete conflict of interest (COI) trainings and complete COI disclosures as listed personnel on IRB submissions.

## **8.14 Funding Source**

This study is funded by the National Institute on Drug Abuse through a Ruth L. Kirschstein National Research Service Award (grant no.1F31DA058452-01, PI: [name]).

## **8.15 Publication Plan**

Per NIH policy ("Final Rule"), trial results must be published to ClinicalTrials.gov no later than 12 months from the study completion date. The Final Rule requires that results information consist of tables of information summarizing: 1) participant flow information, 2) demographics and baseline characteristics of the enrolled participants, 3) primary and secondary outcomes, including results of any scientifically appropriate statistical tests, and 4) adverse events.

Adverse event information consists of one table that summarizes all serious adverse events experienced by participants enrolled in the clinical trial, and a second table that summarizes other adverse events that exceed a frequency of 5 percent in any arm of the clinical trial. The Final Rule adds a third table for summarizing all-cause mortality, with the number and frequency of deaths due to any cause by arm.

A summative manuscript detailing trial feasibility, acceptability, and preliminary effectiveness outcomes will be written and submitted to the peer-reviewed substance use or mHealth literatures. To standardize reporting, the manuscript will adapt the CONSORT 2010 extension to pilot and feasibility studies following guidelines for adaptation in non-randomized studies described by Lancaster & Thabane (2019). The intervention will be described using the TIDieR checklist and guide. The manuscript will be submitted to a peer-reviewed journal within 12 months of study completion.

Findings will also be disseminated to the public during the principal investigator's dissertation defense, and a report summarizing primary results may be shared with stakeholders in the study community.

No participant names or other identifying information will be used in any dissemination materials (published or otherwise).

